9.2 Assessment of Safety

Adverse events will be graded according to the NCI CTCAE v 4.03 (Appendix IV). Adverse events will be summarized by relationship to trial drug, severity and grade. The safety profile of the IPs will be assessed through the recording, reporting and analyzing of baseline medical conditions, adverse events, physical examination findings including vital signs and laboratory tests. Comprehensive assessment of any apparent toxicity experienced by the subject will be performed throughout the course of the trial, from the time of the subject's signature of informed consent. Trial site personnel will report any adverse event (AE), whether observed by the subject.

9.3 Adverse Events

An AE is any untoward medical occurrence in a subject or clinical investigation subject administered a pharmaceutical product, which does not necessarily have a causal relationship with this treatment. An AE can therefore be any unfavorable and unintended sign (including an abnormal laboratory finding), symptom, or disease temporally associated with the use of a medicinal product, whether or not considered related to the medicinal product. In cases of surgical or diagnostic procedures, the condition/illness leading to such a procedure is considered as the AE rather than the procedure itself. In case of a fatality, the cause of death is considered as the AE, and the death is considered as its outcome.

The Investigator is required to grade the severity/intensity of each adverse event. Investigators will reference the NCI-CTCAE v 4.03. This is a descriptive terminology that can be used for adverse event reporting. A general grading (severity/intensity) scale is provided at the beginning of the referenced document, and specific event grades are also provided. If a particular AE's severity/intensity is not specifically graded by the guidance document, the Investigator is to revert to the general definitions of Grade 1 through Grade 5 and use his or her best medical judgment.

The 5 general grades are:

- Grade 1: Mild
- Grade 2: Moderate
- Grade 3: Severe
- Grade 4: Life-threatening or disabling
- Grade 5: Death related to AE. Note: Death (Grade 5 as defined by NCI-CTCAE version 4.03) is mainly regarded as an outcome, to be documented as described below.

According to the Sponsor's convention, if a severity/intensity of Grade 4 or 5 is applied to an AE, then the Investigator must also report the event as a serious adverse event (SAE; see definition below) as per Section 9.10. However, a laboratory abnormality with a severity/intensity of Grade 4, such as anemia or neutropenia, is considered serious only if the condition meets one of the serious criteria described below.

In the case of death, the primary cause of death (the event leading to death) should be recorded and reported as an SAE. "Fatal" will be recorded as the outcome of this respective event; death will not be recorded as separate event. Only if no cause of death can be reported (e.g., sudden death, unexplained death), the death per se might be reported as an SAE.

Investigators must also systematically assess the causal relationship of AEs to the IPs, other medicinal products using the following definitions. Decisive factors for the assessment of causal relationship of an AE to the trial treatments include, but may not be limited to, temporal relationship between the AE and the trial treatments, known side effects of the trial treatments, medical history, concomitant medications and procedures, course of the underlying disease, trial procedures.

Relatedness of an AE will be evaluated as follows:

- Not related: Not suspected to be reasonably related to the IPs. AE could not medically (pharmacologically/clinically) be attributed to the IPs under trial in this clinical trial protocol. A reasonable alternative explanation must be available.
- Related: Suspected to be reasonably related to the IPs. AE could medically (pharmacologically/clinically) be attributed to the IPs under trial in this clinical trial protocol.

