9.5 Serious Adverse Event

An SAE is any untoward medical occurrence that at any dose:

- Results in death.
- Is life-threatening. NOTE: The term "life-threatening" in this definition refers to an event in which the subject is at risk of death at the time of the event; it does not refer to an event that hypothetically might cause death if it were more severe.
- Requires inpatient hospitalization or prolongation of existing hospitalization.
- Results in persistent or significant disability/incapacity.
- Is a congenital anomaly/birth defect.
- Is otherwise considered as medically important.

Important medical events that may not result in death, be life-threatening, or require hospitalization may be considered as SAEs when, based upon appropriate medical judgment, they may jeopardize the subject or may require medical or surgical intervention to prevent one of the outcomes listed in this definition. Examples of such events include allergic bronchospasm requiring intensive treatment in an emergency room or at home, blood dyscrasias or convulsions that do not result in subject hospitalization, or the development of drug dependency or drug abuse.

For the purposes of reporting, any suspected transmission of an infectious agent via an IP is also considered a serious adverse reaction and all such cases should be reported in an expedited manner.

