9.7 Events Not to Be Considered as AEs/SAEs

Medical conditions are present at the initial trial visit that do not worsen in severity or frequency during the trial are defined as Baseline Medical Conditions, and are NOT to be considered AEs. Progression of underlying disease is not an AE and therefore not an SAE per se, rather an efficacy end-point, unless deemed to be causally related to administration of IPs. However, if adverse signs or symptoms occur in association with disease progression then these should be recorded as AEs and reported as SAEs if meeting any seriousness criteria.

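### Sections 9.3 and 9.7 give different recording rules for an unrelated death from disease progression inside the AE reporting window, so whether and how it counts as a fatal SAE depends on which section a site follows

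*Combined protocol and SAP*

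**What the plan says.** Section 9.3 of the protocol treats whatever caused a death as the adverse event: "In case of a fatality, the cause of death is considered as the AE, and the death is considered as its outcome". It then makes reporting mandatory: "In the case of death, the primary cause of death (the event leading to death) should be recorded and reported as an SAE". The one stated departure concerns unknown causes: "Only if no cause of death can be reported (e.g., sudden death, unexplained death), the death per se might be reported as an SAE". Progression is not exempted.

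Section 9.7, which lists what is not to be treated as an AE or SAE, says: "Progression of underlying disease is not an AE and therefore not an SAE per se, rather an efficacy end-point". It qualifies this twice. The first exception is progression "unless deemed to be causally related to administration of IPs". The second concerns what accompanies progression: "if adverse signs or symptoms occur in association with disease progression then these should be recorded as AEs and reported as SAEs", on condition that a seriousness criterion is met. Section 9.5 includes "Results in death" among those criteria.

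Section 9.9 closes AE reporting 30 days after the last dose, or just before another anticancer therapy starts if that comes first. Section 5.2 names SAEs, with treatment-emergent AEs, as Secondary Endpoint 2. Section 11.2.2.3 plans descriptive safety summaries and mentions no tabulation of deaths by cause.

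**The concern.** The treatment phase enrols people with relapsed or refractory squamous NSCLC for whom no curative therapy exists. Some may die of their cancer while on tipifarnib or within 30 days of stopping. The plan should give every site the same instruction for such a death, and the two sections that address it give different ones.

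The synopsis plans 30 centers and up to 18 evaluable subjects, so many sites may treat very few people and differences in site convention would not average out. The trial has no comparator in which the same reporting artifact would show. At stake is the consistency of the SAE and fatal-event counts, and how clearly a reader of the final report can tell deaths from lung cancer from other fatal events.

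**Working it through.** There is no stated figure to reproduce, because the point concerns wording. The check takes each way a death can be recorded and applies sections 9.3 and 9.7 separately.

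| Death as recorded | Section 9.3 | Section 9.7 | Compatible? |
|---|---|---|---|
| Progression, judged related to tipifarnib | Fatal SAE | First exception applies, so it can be an SAE | Yes |
| Fatal sign or symptom of progression (such as respiratory failure) named as primary cause | Fatal SAE under that term | SAE under that term, through 9.5's death criterion | Yes |
| Unrelated progression as primary cause, with a fatal sign or symptom also named | Fatal SAE, term progression | SAE, term the sign or symptom | Counted under both, but under different terms |
| Unrelated progression as primary cause, no serious sign or symptom named | Fatal SAE, term progression | Neither AE nor SAE | No |
| No cause can be reported | Death itself may be reported | Does not apply | No conflict |
| Any death after the 9.9 window closes | Outside AE reporting | Outside AE reporting | Not affected |

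The conflict is therefore confined to the third and fourth rows: unrelated deaths, inside the window, with progression recorded as the primary cause. In the third row the sections disagree on the term. In the fourth they disagree on whether there is an SAE at all.

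For scale, let n be the number of treated subjects and k the number of deaths classified one way under 9.3 and the other under 9.7. The fatal-SAE proportion then shifts by k/n.

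- Input: n = 18, the maximum number of evaluable subjects in section 11.3, taken here as the number treated. This is an assumption.
- k = 1: 1/18 = 5.6 percentage points.
- k = 2: 2/18 = 11.1 percentage points.
- k = 3: 3/18 = 16.7 percentage points.
- If the trial stopped after the first stage with seven treated: k = 1 gives 1/7 = 14.3 percentage points.

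The documents give no value for k, so these figures show sensitivity per death and do not predict a count. The denominator is also uncertain. The safety population in section 11.1.2 is everyone who receives a dose. That can exceed the evaluable number, because the synopsis requires a tissue-confirmed mutation for evaluability while treatment may start on a blood result. A larger n makes each shift smaller.

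**The case against.** The strongest reply is that 9.7 is the specific rule and 9.3 the general one. Its two sentences on progression form a single instruction: progression is not the reportable term, but a serious sign or symptom accompanying it is. A site that reports nothing for a subject who died in respiratory failure from progression has applied only half of 9.7. This stands, and it removes most of the apparent conflict over whether to count a death. It does not remove all of it. The protocol does not say that 9.7 overrides 9.3, the 9.3 instruction is equally explicit, and a death recorded only as progression still gets opposite answers.

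A second reply is that the answer may lie elsewhere. Section 9.3 points to section 9.10 for SAE reporting, and section 9.8 points to the sponsor's eCRF conventions. Neither is in the text available, and either could hold a rule for these deaths. This also stands as a limit on certainty, although 9.3 and 9.7 would still need a cross-reference.

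A third reply is that relatedness is assessed for every AE, that section 9.3 names the course of the underlying disease as a factor in that assessment, and that section 9.2 summarizes AEs by relationship to the drug. A fatal respiratory event from cancer can therefore be shown as unrelated. A reader might infer that the wording lets disease deaths pass as drug toxicity or hides drug-related deaths; because of these provisions, the documents do not support going that far.

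A reader might also infer that the fatal-SAE rate could swing from zero to a quarter or more of subjects. That would need an invented number of progression deaths, and would need every one of them to lack a reportable sign or symptom.

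**Conclusion.** The inconsistency is real but narrow. It covers unrelated deaths within the section 9.9 window whose primary cause is recorded as disease progression. For these, whether the death counts as a fatal SAE, and under what term, depends on the section a site follows and on the term the investigator chooses. It does not extend to every death: later deaths in survival follow-up fall outside AE reporting, and deaths recorded under a serious sign or symptom lead to an SAE under both sections.

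The size is about 5.6 percentage points per affected death, assuming 18 treated subjects; no total can be given. The visible text sets no test or stopping threshold on fatal SAEs, and the ORR analysis is untouched. The conclusion assumes that section 9.10 and the eCRF conventions do not already settle the matter. It is a worthwhile clarification of a secondary safety endpoint and does not threaten the trial's main result.

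**What to change.** First check section 9.10 and the eCRF conventions for an existing rule. Then make 9.3 and 9.7 state one recording rule for deaths from progression, each citing the other. One workable form makes the 9.3 sentence on primary cause of death subject to 9.7, and leaves in place 9.7's existing rule that serious signs or symptoms are reported as SAEs. Nothing here requires that rule to be reversed.

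In 11.2.2.3, add a table of all deaths in the AE reporting window by cause and relatedness, showing deaths from progression separately from other fatal SAEs. Base it on all treated subjects (section 11.1.2). Section 11.2.2.3 now rests on the FAS, which section 11.1.1 lets drop subjects with no post-baseline endpoint data, so an early death could be missed.

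The cost is wording in two sections and one table, with no added visits. The sponsor should confirm that the eCRF captures cause and relatedness for a death from progression that is not entered as an AE. The visible text does not show this, and a field may have to be added. The rule is best settled before deaths are coded, because reclassifying them afterwards in an open-label trial invites bias.

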9.4 Abnormal Laboratory Findings and Other Abnormal Investigational Findings

Abnormal laboratory findings and other abnormal investigational findings (e.g. on an ECG trace) should not be reported as AEs unless they are associated with clinical signs and symptoms, lead to treatment discontinuation or are considered otherwise medically important by the Investigator. If an abnormality fulfills these criteria, the identified medical condition (e.g. anemia, increased ALT) must be reported as the AE rather than the abnormal value itself.

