5.2 Secondary Objectives and Endpoints

Secondary Objective 1: To determine the frequency of HRAS mutations in squamous non-small cell lung cancer (SQ-NSCLC). This objective will be evaluated in the pre-screening phase of the study.

Secondary Endpoint 1: Molecular analyses of tumor and/or cell free DNA samples.

Secondary Objective 2: Safety and tolerability of tipifarnib in subjects with locally advanced unresectable or metastatic, relapsed and/or refractory, squamous non-small cell lung cancer (SQ-NSCLC) with HRAS mutations. This objective will be evaluated in the treatment phase of the study.

Secondary Endpoint 2: Treatment-emergent adverse events (TEAE) and SAEs evaluated according to NCI CTCAE v.4.03.

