7.4 Removal of Subjects from Treatment or Assessment

Subjects may withdraw their consent to participate in this study at any time without prejudice. The Investigator must withdraw from the study any subject who requests to be withdrawn. A subject's participation in the study may also be discontinued at any time at the discretion of the Investigator and in accordance with his/her clinical judgment. Every effort should be made to complete, whenever possible, the tests and evaluations listed for the End of Treatment visit. The Sponsor must be notified of all subject withdrawals as soon as possible. The Sponsor also reserves the right to discontinue the study at any time for either clinical research or administrative reasons and to discontinue participation by an individual Investigator or site for poor enrolment or noncompliance.

Overall, the reasons for which the Investigator or Sponsor may withdraw a subject from study treatment include, but are not limited to, the following:

- Subject experiences disease progression
- Subject experiences unacceptable toxicity
- Subject requires more than 2 dose reductions
- Subject experiences toxicity that is deemed by the Investigator to be no longer safe for the subject to continue therapy
- Subject requests to withdraw from the study treatment
- Subject requires or has taken medication prohibited by the protocol
- Subject is unwilling or unable to comply with the study requirements
- Subject withdraws consent to collect health information
- Subject was erroneously admitted into the study or does not meet entry criteria
- Subject is lost to follow-up
- Subject becomes pregnant

Subjects will return for an End of Treatment visit within approximately 30 days after the last administration of the study drug (or sooner if another anticancer therapy is to be initiated). If a subject fails to return for scheduled visits, a documented effort must be made to determine the reason. If the subject cannot be reached by telephone after 2 attempts, a certified letter should be sent to the subject (or the subject's legally authorized representative, if appropriate) requesting contact with the Investigator. This information should be recorded in the study records.

The Investigator must obtain documented consent from each potential subject prior to participating in a clinical trial. This trial has two consents forms, one per pre-screening phase and another per treatment phase.

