8 TREATMENTS

Subjects enrolled in the treatment phase will receive tipifarnib as monotherapy in this study. In the absence of unacceptable tipifarnib related emergent toxicity or disease progression, subjects may receive treatment with tipifarnib for up to 24 months at the discretion of the Investigator. Treatment beyond 24 months may continue upon agreement of the Investigator and the Sponsor. The Sponsor or its designee will provide the study site with a supply of tipifarnib sufficient for the completion of the study.

All study subjects will be also eligible to receive best supportive care (BSC) defined as any standard supportive measures that are not considered a primary treatment of the disease under study, including the use of growth factors (i.e. GCSF) for myelosuppression. BSC will be provided by the study sites.

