11.2.2 Safety and Tolerability

11.2.2.1 Subject Adherence

Number of treatment cycles per subject will be summarized by numbers and percents of subjects who received each number of treatment cycles.

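### Section 9.4 lets asymptomatic laboratory abnormalities that change dosing or need corrective treatment enter the TEAE data only at the investigator's discretion.

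*Combined protocol and SAP*

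**What the plan says.** Section 5.2 makes safety and tolerability Secondary Objective 2, with one stated endpoint: "Treatment-emergent adverse events (TEAE) and SAEs evaluated according to NCI CTCAE v.4.03".

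Three places govern whether a laboratory abnormality becomes part of that endpoint.

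- Section 9.3 gives the general definition, tied to use of a medicinal product: "An AE can therefore be any unfavorable and unintended sign (including an abnormal laboratory finding), symptom, or disease temporally associated with the use". It sets no further condition. It also says that a Grade 4 laboratory abnormality, with anemia and neutropenia as examples, is serious only if a seriousness criterion is met.
- Section 9.4 gives the reporting rule. Abnormal laboratory findings "should not be reported as AEs unless they are associated with clinical signs and symptoms, lead to treatment discontinuation or are considered otherwise medically important". That last judgement is the investigator's. If one of these conditions is met, "the identified medical condition (e.g. anemia, increased ALT) must be reported as the AE rather than the abnormal value itself".
- Section 9.8 lists what an AE report must contain, including treatment given and any action taken with the study drug. Dose modification is thus an attribute of an AE already reported; it does not trigger a report.

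The protocol expects the events in question. Section 8 allows supportive care "including the use of growth factors (i.e. GCSF) for myelosuppression", and section 7.4 lists "Subject requires more than 2 dose reductions" among the reasons for stopping study treatment.

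On analysis, section 11.2.2.3 plans descriptive safety summaries. Section 11.2.2.1 summarises exposure by cycles: "Number of treatment cycles per subject will be summarized by numbers and percents of subjects who received each number of treatment cycles".

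**The concern.** The 9.4 list leaves out the events that most often signal a tolerability problem without symptoms: a dose held, delayed or reduced, and a treatment given to correct the abnormality. In such a case the only open route into the AE data is the investigator's opinion of importance. One site may record every such cytopenia and another none, both complying with the protocol.

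What is at stake is the hematologic part of the TEAE table in a single-arm trial of about 18 subjects. Because 9.4 works by telling sites not to report, any error runs one way, towards a more favourable safety profile. An event that is not an AE also falls outside three requirements tied to AEs: the causality assessment (9.3), the record of action taken (9.8) and follow-up to stabilization (9.12).

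**Working it through.** The plan states no figure here, so the check is to follow one case through the rules and then give the scale.

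**Case.** A subject has a Grade 3 or 4 neutropenia without symptoms, the dose is held or reduced, and treatment then continues.

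| Rule | Applied to the case | Result |
|---|---|---|
| 9.3, general AE definition | A laboratory finding can be an AE | Permits recording |
| 9.4, clinical signs and symptoms | None | Not met |
| 9.4, treatment discontinuation | Treatment continues | Not met |
| 9.4, medically important | Left to the investigator | Discretionary |
| 9.3, Grade 4 or 5 reported as SAE | Laboratory abnormalities are exempted unless a seriousness criterion applies | No automatic route |
| 9.8, action taken | Completed on an AE report | Does not create a report |

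No row makes recording mandatory.

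**Same case with corrective treatment.** Suppose a growth factor is given, or an anemia is transfused. Section 9.5 describes important medical events as including those that may need intervention to prevent a serious outcome, and names blood dyscrasias without hospitalization as an example. An investigator using that guidance would probably find the third condition of 9.4 met. But 9.5 defines seriousness, says such events may be so considered, and rests on medical judgement. Capture is likely, not required. The similar wording can also work the other way: a site that equates medical importance in 9.4 with the seriousness criterion in 9.5 would record only serious cytopenias, and the non-serious Grade 4 event foreseen in 9.3 would go unrecorded.

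**Spread over sites.** The synopsis plans 30 centers and up to 18 evaluable treated subjects, which is 18/30 = 0.6 per center. The TEAE table will therefore combine the readings of many investigators, most with one subject or none.

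**Scale.** If k of n treated subjects have an unrecorded event, the reported incidence falls by k/n. With n = 18 (sections 11.2.1 and 11.3):

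- k = 1: 1/18 = 5.6 percentage points
- k = 2: 2/18 = 11.1 percentage points

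If the trial stops after stage one with n = 7, k = 1 gives 1/7 = 14.3 points. These figures show sensitivity only. The documents contain no cytopenia rate and no basis for estimating k.

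**The case against.** The strongest reply is that little is really lost.

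- *Laboratory data remain.* Section 9.2 bases the safety profile on laboratory tests as well as AEs, and section 11.1.2 sets inclusion and change-from-baseline rules for laboratory parameters. Section 11.2.2.2 tabulates each concurrent medication, so growth-factor use would be visible. Tablet counts and dosing diaries are kept under 8.8. This stands: the loss is confined to the AE data. It does not remove the point, because the named endpoint is TEAEs and SAEs. A laboratory value or a medication count also carries no causality assessment and no link to a dose change.
- *Section 9.5 guides the term.* This stands for most cases with corrective treatment, as shown above. It does little for a case where the dose is only held or reduced.
- *Sections 9.3 and 9.4 need not conflict.* One can be read as the definition and the other as the operating rule. That is fair; they call for alignment and are not a flat contradiction.
- *Unseen text may help.* Section 8.5 on dose modification and section 9.10 on SAE reporting are not in the public text. Section 9.8 refers to eCRF conventions for specific guidance, and section 11 defers analysis details to a SAP. Any of these could add a reporting instruction or a table.

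For that last reason, a reader might infer that dose modifications would have no recorded cause. The documents do not support this: section 8.5 or the eCRF may require a reason for each change. What can be said is that a modification may have no linked AE.

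**Conclusion.** The point holds as a matter of discretionary capture. Under 9.4 as written, an asymptomatic laboratory abnormality that leads to a dose hold, delay or reduction, or to corrective treatment, has no mandatory route into Secondary Endpoint 2. Hematologic TEAEs may be under-recorded, to a degree that varies by site and only in the downward direction. Each subject affected costs 5.6 percentage points at n = 18. The primary ORR analysis is not touched.

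This rests on the public text being complete on AE triggers, and on some such events being asymptomatic and judged unimportant. The first could be overturned by section 8.5 or the eCRF conventions; the second cannot be quantified.

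Two stronger readings are tempting. A reader might infer that the TEAE rate for cytopenias could be driven close to zero; that would need nearly every investigator to dismiss nearly every dose-changing cytopenia, and nothing in the documents supports it. A reader might also infer that every Grade 3 or higher laboratory value has to be an AE; no section says so, and such a trigger would be a preference, not the repair of a defect.

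**What to change.** 1. **Section 9.4.** Add that a laboratory abnormality is also recorded as an AE when it leads to interruption, delay or reduction of study drug, or to corrective treatment such as a growth factor or transfusion. In 9.3, refer to the 9.4 conditions so that definition and reporting rule agree.
2. **Section 11.2.2.3.** Tabulate the worst post-baseline CTCAE grade for each laboratory parameter, using the laboratory data already collected. This table does not depend on any site's reading of 9.4.
3. **Section 11.2.2.3.** Summarise dose modifications due to AEs from the action-taken item in 9.8, since the cycle count in 11.2.2.1 shows neither holds nor reductions.

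If section 8.5, the eCRF conventions or the SAP already contain any of these, a cross-reference is enough.

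The cost is one sentence, one alignment and two tables. The downside is a few extra AE entries in about 18 treated subjects and a somewhat less favourable TEAE table. The changes concern recording and tabulation only and leave the dosing rules as they are.
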